6.1.2. Deviations, Missing Concentrations and Anomalous Values

Subjects who experience events that may affect their PK profile (eg, incomplete dosing due to injection reactions) may be excluded from the PK analysis.

In summary tables and plots of median profiles, statistics will be calculated having set concentrations to missing if 1 of the following cases is true:

1. A concentration has been collected as ND (ie, not done) or NS (ie, no sample);
2. A deviation in sampling time is of sufficient concern or a concentration has been flagged anomalous by the pharmacokineticist.

Note that summary statistics will not be presented for any time point at which more than 50% of the data are missing.

6.1.3. Pharmacokinetic Parameters

Actual PK sampling times will be used in the derivation of PK parameters.

If a PK parameter cannot be derived from a subject's concentration data, the parameter will be coded as NC (ie, not calculated). (Note that NC values will not be generated beyond the day that a subject discontinues.)

In summary tables, statistics will be calculated by setting NC values to missing; and statistics will be presented for a particular dose with ≥ 3 evaluable measurements.

7. STATISTICAL METHODOLOGY AND STATISTICAL ANALYSES

7.1. Statistical Methods

The statistical summaries are non-inferential. The data are summarized by cohort defined by the initial dose of the study drug.

7.1.1. Analyses for Continuous Data

Continuous data will be summarized using with the mean, median, minimum, maximum and standard deviation. Missing values will be excluded from the analysis.

7.1.2. Analyses for Categorical Data

Categorical data will be summarized by number of unique patient incidence. Missing data will be excluded from the analysis.

7.1.3. Analyses for Binary endpoints

Binary data will be summarized using number of unique patient incidence, and confidence interval for binomial proportions may be presented

7.1.4. Analyses for Time-to-Event endpoints

Time- to- event endpoint will be analyzed using Kaplan- Meier estimates.

7.2. Statistical Analyses

7.2.1. Primary Endpoints Analysis

The primary analysis will be based on the Full Analysis Set. The analysis is to summarize the adverse event incidence and will implement Pfizer standard summaries for adverse events. The occurrence of DLTs observed in the dosing cohorts is used to estimate the MTD as described in the [Study Design](#) section. Adverse Events constituting DLTs will be listed per dose level. Because the intent is to find a desirable dose that meets the tolerability criteria based on DLT rate while demonstrating clinical activity based on response rate, descriptive statistics (n, frequency, and percentage) will be reported. Corresponding listings of data will be generated.

7.2.2. Secondary Endpoints Analyses

Analysis of Progression Free Survival, a “time to event endpoint,” will define time from the baseline date. Summaries of n and % of patients with PFS, and data listing will be generated. If sufficient numbers of patients are available, the PFS will also be summarized using the Kaplan Meier method. PFS rates at 6 months, 1 year and 2 years will be estimated using Kaplan Meier Method. Summary statistics (N, mean, SD, min, max) and data listings will be prepared for duration of Stable Disease (SD), and duration of Response (DR). Similar approach will be applied to Overall Survival (OS).

Percentage of tumor burden change from baseline will be summarized according to scheduled events.

Summary statistics and data listings of raw values and changes in immunohistochemistry (IHC) assessment of tumor-infiltrating lymphocytes (including but not limited to CD4 and CD8) in paired tumor biopsy collected at pre and post-treatment time points will be prepared.

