21. Tumor Assessments: Tumor assessments will include all known or suspected disease sites. Imaging may include chest, abdomen and pelvis computed tomography (CT) or magnetic resonance imaging (MRI) scans. Brain scans and bone scans will be performed at baseline and on-study if disease is suspected or has been previously documented as appropriate to follow disease. Baseline central nervous system (CNS) imaging is not required with the exception of symptomatic patients to rule out CNS metastases. CT or MRI scans to be done every 6 weeks (±5 days) from the start of study treatment until confirmed disease progression by RECIST (1.1), irRECIST or death, or patient begins a different anti-cancer therapy. Scans may be moved to every 12 weeks after 24 weeks until confirmed progressive disease. Tumor assessments should be fixed according to the calendar, regardless of treatment delays. Confirmation of response (complete response (CR)/partial response (PR)) is not required. CT or MRI scans should be completed before tumor biopsy samples are collected.

- 24. PK Sampling: Specific timing for collection of pharmacokinetic samples can be found in the pharmacokinetic and pharmacodynamic sampling schedule table below.
- 25. Anti-drug antibodies: Specific timing for collection of anti-PF-04518600 and anti-utomilumab antibody samples can be found in the Pharmacokinetic and Pharmacodynamic Sampling Schedule table below.

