## 1.2.1.4. PF-04518600 Clinical Efficacy

As of data cutoff date of 24 May 2017, 2 confirmed partial responses (PRs) were reported in Study B0601002 Part A1; 1 PR was reported in a cutaneous melanoma patient treated at 0.1 mg/kg dose level who had a duration of response of 10.3 weeks, and a second PR was reported in a hepatocellular carcinoma (HCC) patient treated at 0.3 mg/kg dose level who had a duration of response of 44.1+ weeks and is still on study drug. A total of 27 (51.9%) patients, of the 49 evaluable patients treated in Part A1, experienced a best overall response of stable disease (SD).

As B0601002 is an ongoing study, the available data are preliminary in nature and are subject to further review and quality control and may therefore change.

[figure not shown]

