# 7.4. Tumor Response Assessments

Tumor assessments will include all known or suspected disease sites. Imaging may include chest, abdomen and pelvis computed tomography (CT) or magnetic resonance imaging (MRI) scans; brain CT or MRI scan for patients with known or suspected brain metastases; bone scan and/or bone X-rays for patients with known or suspected bone metastases.

The same imaging technique used to characterize each identified and reported lesion at baseline will be employed in the subsequent tumor assessments.

Anti-tumor clinical activity will be assessed through radiological tumor assessments conducted at baseline, during treatment as specified in the applicable Schedule of Activity, whenever disease progression is suspected (eg, symptomatic deterioration), until confirmed progressive disease or start of subsequent anticancer therapy whichever comes first.

Assessment of tumor response will be made using RECIST version 1.1 (Appendix 5) and irRECIST response criteria (Appendix 6). 86,87

All patients' files and radiologic images must be available for source verification and for potential peer review.

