6. HANDLING OF MISSING VALUES

Missing data will be excluded from the tabular summaries.

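### Later-visit summaries of percent tumour-burden change will understate growth, because scans stop at confirmed progression and missing values are simply dropped

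*SAP*

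**What the plan says.** SAP 7.2.2 plans one summary of continuous tumour change: "Percentage of tumor burden change from baseline will be summarized according to scheduled events". SAP 7.1.1 supplies the statistics and the missing-data rule: "Continuous data will be summarized using with the mean, median, minimum, maximum and standard deviation. Missing values will be excluded from the analysis". The number of patients contributing is not in that list. SAP 6 repeats the general rule: "Missing data will be excluded from the tabular summaries".

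Protocol 7.4 fixes when scanning ends: "until confirmed progressive disease or start of subsequent anticancer therapy whichever comes first". The Part B1 schedule footnote on tumour assessments is similar: "until confirmed disease progression by RECIST (1.1), irRECIST or death, or patient begins a different anti-cancer therapy". Scans are every 6 weeks in A1 and B1 and every 8 weeks in A2 and B2, with 12-week intervals possible or planned after Week 24. Protocol 5.4.6 asks for a repeat scan at least 4 weeks after first progression, so patients stay under assessment until progression is confirmed.

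The readable SAP text names no best-change, first-scan or individual-curve display. Appendix 1.4, on non-standard figures and tables, reads TBD. Blacked-out text may contain more.

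**The concern.** A patient's later values are missing because that patient's tumour grew. Averaging the values that remain selects on the quantity being averaged. The by-visit figure answers what the change is among patients still being scanned, whereas the secondary objective concerns activity in the patients treated.

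The SAP recognises this kind of problem elsewhere. Section 5.8 describes deaths in the TTP analysis as informative censoring, and Section 6.1.2 suppresses PK statistics when more than half the data at a time point are missing. Tumour burden has neither safeguard. With about 10 patients per expanded A1 dose level and up to 20 per A2 arm, a late mean can rest on a handful of patients without the table showing it. Summaries are by initial dose (SAP 7.1), so a reader will naturally set the 30 mg and 250 mg arms side by side, and an arm that loses patients to progression faster is flattered more.

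**Working it through.** The plan states no figure for this summary, so there is nothing to reproduce. The check concerns direction and size.

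**Inputs from the documents.** Scan weeks are 6/12/18/24 (A1) and 8/16/24 (A2). Progression is a rise of at least 20% over nadir. Removal is after confirmed progression.

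**Assumed inputs.** Log tumour size at week *t* is *g·t* plus measurement error with SD 0.08. The growth rate *g* is normal across patients, mean 0.025 and SD 0.025 per week. Confirmation is at the next scheduled scan.

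**Plausibility.** At Week 6 the log change has mean 0.15 and SD √(0.15² + 0.08²) = 0.17. The chance of exceeding ln 1.2 = 0.182 is Φ((0.150 − 0.182)/0.17) ≈ 43%. Protocol 1.2.1.4 reports: "A total of 27 (51.9%) patients, of the 49 evaluable patients treated in Part A1, experienced a best overall response of stable disease". With 2 partial responses, 49 − 27 − 2 = 20 patients, or 41%, had neither. This is only a rough match, since those 20 need not all have progressed at the first scan. (The printed 51.9% is 27/52; 27/49 is 55.1%.)

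**All-patient mean.** exp(0.025*t* + (0.025²*t*² + 0.08²)/2) − 1. At Week 24: exp(0.6 + (0.36 + 0.0064)/2) − 1 = exp(0.783) − 1 ≈ +119%. The other weeks follow in the same way.

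**Observed mean** in patients still scanned, by simulation of 400,000 patients:

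| Schedule | Week | Still scanned: mean | All patients: mean |
|---|---|---|---|
| A1 | 6 | +18% | +18% |
| A1 | 12 | +42% | +42% |
| A1 | 18 | +27% | +74% |
| A1 | 24 | +5% (36% of patients) | +119% |
| A2 | 8 | +25% | +25% |
| A2 | 16 | +62% | +62% |
| A2 | 24 | +23% (48% of patients) | +119% |

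The first two scans agree. From the third, the observed curve falls while average tumour size rises. In a 20-patient A2 arm, 48% is about 10 patients; in a 10-patient A1 cohort, 36% is about 4.

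**Sensitivity**, from a separate simulation with scans at Weeks 8/16/24/36/48 and no drug effect. Its two growth settings were chosen to agree with the placebo PFS of 1.5 to 2.8 months cited in protocol 1.2.5.3.
- Log growth 0.25 per 8 weeks (SD 0.15): Week 24 +42% observed against +135%; Week 36 +18% against +287%.
- Log growth 0.15 per 8 weeks (SD 0.15): Week 24 +26% against +74%; Week 36 +6% against +147%.
- If progression is confirmed by an extra scan 4 weeks later, the Week 24 observed means fall to +11% and +3%, and the bias begins at the second scan (Week 16: +26% against +73% in the faster setting).
- If every tumour grows and none shrinks, observed late medians level off at about +18% to +46%, while all-patient Week 48 medians are +44% to +233%.

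**Contrast between groups.** With an active drug (log growth −0.08 per 8 weeks) and confirmation at the next scheduled scan, the Week 24 mean is −18% observed (95% still scanned) against −13% in all patients. The gap to the faster no-effect setting is 42 + 18 = 60 points observed, against 135 + 13 = 148 in all patients. For the slower setting it is 26 + 18 = 44 against 74 + 13 = 87. The by-visit table compresses the difference by half or more.

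**The case against.** Several limits stand.

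- A reader might infer that later visits contain only patients who have not progressed. The stopping rule is confirmed progression, so patients with unconfirmed progression are still scanned. In the second simulation they were 10% to 58% of those scanned at Week 24 when confirmation waited for the next scheduled visit. A model that stops scans at first progression gives −11% at Week 24 on the A1 schedule, but the protocol has no such rule.
- A reader might infer that the table shows tumour control whatever the drug does. It does not: on the A2 schedule above, every mean through Week 24 shows growth, and without shrinking tumours the result is a false plateau. An active drug still shows in the early visits and in the numbers remaining.
- A reader might infer that the table drives the RP2D. Protocol 3.6 rests that choice on MTD feasibility, safety, pharmacodynamic effects and the OBD. SAP 7.2.1 ties activity to response rate, and the B2 ten-patient rule counts responders. SAP 7.1 calls the summaries non-inferential, and no test between the A2 arms is planned.
- Early progressors are kept elsewhere: ORR and disease control use the analysis-set denominator, and PFS and TTP count progression. That limits the harm but does not correct this table.
- The all-patient mean is an extrapolation past progression, new therapy and death, so it is a yardstick, not an observable target. Progression through non-target or non-measurable lesions need not raise the measured sum, so loss may be less tied to burden than modelled. SAP Table 2 does count new measurable lesions in tumour burden, which keeps part of that link.
- Expected treatment is 12 to 18 weeks, so many scans precede the affected visits.

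**Conclusion.** The point holds in limited form. By-visit means and medians of percent tumour-burden change are biased toward less growth from about the third scan, or from the second if progression is confirmed at an extra 4-week scan. The first post-baseline scan is essentially free of this mechanism. Under the assumed rates the Week 24 mean is about +5% (A1 schedule) or +23% (A2 schedule), against about +119% for all patients. The direction follows from the documents. The size rests on assumed growth rates, their spread, measurement error and the timing of confirmation. Because the table is secondary and descriptive and feeds no stated decision rule, this is a cheap improvement to the SAP, not a threat to the trial's conclusions.

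**What to change.** In SAP 7.2.2:

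1. Restrict by-visit means and medians to the first scheduled post-baseline scan (Week 6 in A1/B1, Week 8 in A2/B2). Count patients who die or progress clinically before it as a separate category in the denominator.
2. Add best percent change per patient (waterfall plot), stating how many have no post-baseline scan.
3. Add individual curves over time (spider plot) that keep the scan showing progression.
4. If later-visit summaries are kept, show n and the reasons for leaving at each visit, and label them as conditional on remaining under assessment.

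The cost is SAP wording and two standard figures from data already collected. The drawback is that best change takes each patient's minimum and is itself favourable, so it should be read beside the first-scan summary.

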7.2.3. Safety Analyses

Safety data will be summarized using Pfizer standard data summary procedures.

Data will be summarized by cohort, defined by the initial dose. When the initial dose is determined to be the MTD, then the tables will also label the dose as the MTD.

A breakdown of demographic data will be provided for age, race, weight, body mass index, height, and tumor type by cohort defined by initial dose if data permits.

Adverse Events

Adverse Events (AEs) will be graded by the investigator according to the CTCAE version 4.03 and coded using the MedDRA. The focus of AE summaries will be on Treatment Emergent Adverse Events, those with initial onset or increasing in severity after the first dose of study medication. The number and percentage of patients who experienced any AE, serious AE (SAE), treatment related AE, and treatment related SAE will be summarized according to worst toxicity grades. The summaries will present AEs both on the entire study period and by cycle (Cycle 1 and Cycles beyond 1). The Safety Analysis Set will be used.

Laboratory Tests Abnormalities

The number and percentage of patients who experienced laboratory test abnormalities will be summarized according to worst toxicity grade observed for each laboratory test. The analyses will summarize laboratory tests both in the entire study period and by cycle (Cycle 1 and Cycles beyond 1). Shift tables will be provided to examine the distribution of laboratory abnormalities. The Safety Analysis Set will be used.

For laboratory tests without CTC grade definitions, results will be categorized as normal, abnormal high/low or not done.

Study Conduct and Patient Disposition

An accounting of the study patients will be tabulated. The subject evaluation groups will be listed. The Full Analysis Set will be used.

Subject discontinuation from treatment and study will be tabulated and listed separately with their reason for discontinuation. The Safety Analysis Set will be used.

Baseline Characteristics

Baseline characteristics such as demographics, prior medication, medical history, ECOG performance status, and primary diagnosis will be tabulated and listed. For ECOG performance status a shift table (worst post-baseline vs baseline may be produced). The Safety Analysis Set will be used.

Treatment Administration/Compliance

Listings and tables by dose level will be provided. Cycle length is 14 days. Day 1 of a cycle is the first date of dose within that cycle. The safety analysis set will be used.

Dose modifications may occur in the following ways:

- Cycle delay—Day 1 of current cycle starts later than 14 days from Day 1 of the previous cycle (only applies to cycle 2 and above);
- Dose reduction—A decrease in the administered total daily dose (non-zero) compared to the planned total daily dose upon enrollment. If in the CRF the prescribed dose unit is mg/kg, but the actual dose is in mg the actual dose mg/kg should be calculated considering the body weight of the patient at that visit.

Intra-patient dose escalation is not allowed in this study. The following will be summarized by subject for each dose level:

- Number of subjects per dose level;
- Median and range of number of cycles started per subject;
- Number (%) of subjects starting a cycle (1, 2, 3...);
- Number (%) of subjects with cycle delays;
- Number (%) of dose interruptions (include both known and unknown dates);
- Number (%) of subjects with dose reductions;
- Number (%) of each reason (AE vs. Other) for cycle delays, dose interruptions and dose reductions;
- Time on treatment (median, range).

The following will be summarized by cycle received for each dose level:

- Total number of cycles started;
- Number of cycles started per subject (median, range);
- Number of cycles before 1st delay (median, range);
- Number of cycles before 1st reduction (median, range);
- Number of cycles before 1st interruption (median, range).

The following will be summarized for cumulative dose by dose level and cycle:

- Summary statistics (mean, median, standard deviation and range) of cumulative dose and percent of starting dose (compared to Day 1 dose of each cycle).

Listings by subject (ordered by dose level): start date and stop date of each dosing period within each cycle (including records with 0 mg), administered total daily dose for each period, any missed doses with unknown dates (Y/N), number of missed doses with unknown dates, reason for any dosing changes.

Listings by subject and each cycle (ordered by dose level): cycle length, total planned dose, administered total dose, percentage of planned dose, dose delay (yes/no), dose reduction (yes/no), and dose interruption (yes/no).

Prior, Concomitant, and Further Therapies

Prior, concomitant, and further therapies (drug and non-drug treatments) will be coded by the World Health Organization (WHO) medical dictionary. Listings of prior, concomitant, and further therapies will be provided separately.

The following data will also be summarized by treatment and in accordance with the current sponsor reporting standards:

Discontinuations, Adverse Events, laboratory data, vital signs, ECG and concomitant medication data will be summarized by cohort defined by initial dose in accordance with current Pfizer data standards.

It should be recognized that most studies are not designed to reliably demonstrate a causal relationship between the use of a pharmaceutical product and an adverse event or a group of adverse events. Except for select events in unique situations, studies do not employ formal adjudication procedures for the purpose of event classification. As such, safety analysis is generally considered as an **CCI** [REDACTED] and its purpose is to generate hypotheses for further investigation.

Cytokine Release Syndrome

Patient incidence and percentage of cytokine release syndrome will be tabulated by dose received. Further assessments on the impact on the tumor response may be performed when data warranted.

Electrocardiograms (ECG)

TriPLICATE 12-lead ECGs will be performed per Schedule of Activities. The Day 1 triPLICATE ECG prior to treatment administration will be used as baseline; if it is missing, values from the single ECG taken at screening will be used for baseline.

The following will be presented:

1. Summaries of quantitative results (QT, QTc, RR, PR, QRS, heart rate) and changes from baseline will be summarized by visit for all scheduled visits. For triplicate ECGs, the mean of the three ECGs will be used as the value for each parameter. Results of ECGs done as additional follow-up for prolonged PK t1/2 and unscheduled ECG results will be listed but not summarized.
2. Summaries of qualitative results (normal; abnormal, not clinically significant [NCS]; abnormal, clinically significant [CS]; and unevaluable) will be summarized by visit for all scheduled visits. For triplicate ECGs, the most serious evaluation (abnormal CS, abnormal NCS, unevaluable, normal) of the triplicate tests will be used.
3. Shift tables based on interpretation (normal; abnormal, NCS; abnormal, CS; and unevaluable) will be prepared for baseline versus the final scheduled ECG.

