Cardiac enzymes		X					X		X (Cycle 5 only)	X	X (Cycle 9 and every other cycle)	X								
Alpha Fetoprotein for HCC patients only	X							Ev	very 6 weeks											

Part A1 Monot	therapy						Trea	ıtmer	t Period							Po	ost Tr	eatment		
		Cycl (Day			(D		(Day			(Days	Subsequent Cycles (Days 1 to 14) 	End of Treatment (EOT) 	-		(	Days	Follo after	w Up EOT visit) 		
Visit Identifier	Screen¹ (≤28 days)	Day 1	Day 2	Day 8	Day 1	Day 8	Day 1	Day 8	Day 1	Day 1	Day 1			28 to 35 days	days	56 days	70 days	84 days		
Visit Window in Days	•		±1	±1	±2	±2	±2	±2	±2	±2	±2									
Registration and Treatment																				
Registration  PF-04518600 Tr eatment 		X			X		X		X	X	X									
Tumor Assessments																				
CT or MRI scan or equivalent 	X	Е	very								may be moved sive disease.	to every								
Other samplings	loces																			
CCI									,											
Blood Samples for PK 								Se	ee Pharmacol	kinetic and	Pharmacodyna	amic Samplir	ng Sch	nedule	Table	below	•			
Blood Sample for Anti-PF-045186 00 Antibodies 								Se	ee Pharmacol	kinetic and	Pharmacodyna	amic Samplir	ng Sch	nedule	Table	below				
CCI																				

Part A1 Monot	therapy						Tre	atmer	it Period							Po	ost Tr	eatment			
		Cyc (Day			(D		(Day	cle 3 s 1 to 4)	-	(Days	Subsequent Cycles (Days 1 to 14) 	End of Treatment (EOT) 			(	Days		w Up EOT visit) 			
Visit Identifier	Screen¹ (≤28 days)	Day 1	Day 2	Day 8	Day 1	Day 8	Day 1	Day 8	Day 1	Day 1	Day 1		14   28 to days   42   56   70   84 days   days days days days days days days days								
Visit Window in Days			±1	±1	±2	±2	±2	±2	±2	±2	±2										
Other clinical assessments																					
Adverse Events 	X	X	X	X	X	X	X	X	X	X	X	X	X	X	X	X	X	X			
Concomitant Medication and non-drug supportive interventions 	X	X	X	X	X	X	X	X	Х	X	X	X	X   X   X   X   X   X   X   X   X   X								
Echocardiogram or MUGA 	X					•	Ev	very 3	months			X									

Except for safety assessments, all other activities performed during Cycle 1 can be performed  $\pm 1$  day, and for Cycle 2 onwards  $\pm 2$  days. Safety assessments must be performed prior to dosing (see footnotes for details).

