#### 5.4. Administration

## 5.4.1. Part A1 Monotherapy

PF-04518600 will be administered intravenously with adjustment for body weight at every cycle. A cycle is defined as the time from Day 1 dose to the next Day 1 dose. If there are no treatment delays, a cycle will be 2 weeks in duration. PF-04518600 will be administered on Day 1 of each 2 week cycle per the IP Manual as an intravenous (IV) infusion over 60 minutes (-5 to +15 minutes and should include the time needed to flush the infusion line) on an outpatient basis. If infusion reaction occurs, infusion rate maybe reduced (refer to Section 5.4.5.1 Infusion Reactions and Appendix 4 for management of infusion reactions).

The use of an infusion pump is the preferred method of administration to ensure accurate delivery of the investigational product, but gravity drips are allowed.

Each patient may receive PF-04518600 until disease progression by irRECIST (see Section 5.4.6 Treatment After Initial Evidence of Radiological Progression), patient refusal, or unacceptable toxicity occurs, or end of study, whichever occurs first.

The dose level will be assigned by the sponsor (Section 5.1 Allocation to Treatment). Patient actual body weight will be used to calculate the mg/kg dose, and the calculated dose will be rounded off to the second decimal point. All patients should be weighed within 72 hours prior to dosing for every cycle to ensure they did not experience either a weight loss or gain >10% from the prior weight used to calculate the amount of PF-04518600 required for dose preparation. Decision to recalculate PF-04518600 dose based on the weight obtained at each cycle can be in accordance with institutional practice, however if the patient experienced either a weight loss or gain >10% compared to the weight used to calculate the initial dose, the amount of PF-04518600 required for investigational product preparation and administration for the current cycle must be recalculated using this most recent weight obtained.

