# 5.4.5.6.2. Part B Combination Therapy

Intrapatient dose reductions are not permitted during the combination therapy with PF-04518600 and utomilumab unless, in discussion with the sponsor, a dose combination level is deemed to be above the determined MTD for the combination.

Given the expected similarities of side effect profile and mechanism between the two co-stimulation monoclonal antibodies, both treatments must be interrupted or discontinued together. Patients will not be permitted to continue treatment with one agent, while the other agent is either interrupted or permanently discontinued. If infusion related reactions are observed following the administration of the first agent, administration of the second agent will be withheld until symptoms resolve (see Section 5.4.5.1 Infusion Reactions).

Treatment of irAEs should follow guidelines set forth in Table 4 in Section 5.4.5.4 Recommended dose modifications for any other drug-related toxicity are illustrated in Table 6.

Table 6. Treatment Interruptions/ Discontinuations for Drug Related Toxicity at Start of Subsequent Cycle

Toxicity	NCI CTCAE Severity Grade	Treatment Modifications
Hematologic abnormalities.	Grade 3	
 
Withhold until recovery to Grade 1 or better.
 
If toxicity does not resolve to Grade 1 or better within 4 weeks of last infusion, consider permanent discontinuation after consultation with the sponsor.
 
Upon the second occurrence of the same Grade 3 toxicity that does not resolve to Grade ≤1 by the next administration, treatment must be permanently discontinued.
 

	Grade 4	Permanent discontinuation.     Exceptions are:     Single laboratory values out of normal range that are unlikely related to investigational product (s) as assessed by the Investigator, do not have any clinical correlate, and resolve within 7 days with adequate medical management.
Infusion-related reaction.	Grade 1-4	• See Section 5.4.5.1 and Appendix 4.
Hypersensitivity reaction.	Grade 1-4	• See Section 5.4.5.2 and Appendix 4.

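### SAP 7.2.3 scores some protocol-compliant dosing as cycle delays (all parts) and as dose reductions (weight-based dosing), inflating the all-cause counts

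*SAP*

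**What the plan says.** **SAP 7.2.3, Treatment Administration/Compliance.** Cycle length is set at 14 days. A cycle delay, from Cycle 2 on, occurs when "Day 1 of current cycle starts later than 14 days from Day 1 of the previous cycle". A dose reduction is "A decrease in the administered total daily dose (non-zero) compared to the planned total daily dose upon enrollment". If the CRF has mg/kg prescribed but mg given, "the actual dose mg/kg should be calculated considering the body weight of the patient at that visit". These definitions feed, by dose level, the number (%) of subjects with delays and with reductions, the number of cycles before the first of each, a table of reasons (AE versus Other), and yes/no flags in a by-cycle listing.

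**Protocol, timing.** The Schedule of Activities tables for all parts give Day 1 of Cycle 2 and later cycles a ±2-day window. The note under the Part A1 table says that, safety assessments aside, "all other activities performed during Cycle 1 can be performed" one day either side, and two days either side from Cycle 2. Sections 5.4.1 to 5.4.4 describe an undelayed cycle as two weeks. The Document History entry for Amendment 3 gives the window as the reason for saying two weeks instead of 14 days.

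**Protocol, weight.** Section 5.4.1 (Part A1) says "Decision to recalculate PF-04518600 dose based on the weight obtained at each cycle can be in accordance with institutional practice". Recalculation becomes mandatory "if the patient experienced either a weight loss or gain >10% compared to the weight used to calculate the initial dose". The same section opens by describing weight adjustment at every cycle, and footnote 7 of the Part A1 and B1 schedules reads the same way.

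**The concern.** The SAP rules are stricter than the dosing rules they describe. Protocol 5.4.5 presents between-cycle delay as a response to persisting toxicity. Section 5.4.5.6.1 presents a Part A reduction as a step of one or two dose levels for toxicity. Under the SAP definitions, an appointment moved by a day, or a small weight gain on an unchanged mg dose, enters the same count. A reader comparing dose levels on the percentage of subjects delayed or reduced, or on how early the first event came, would see real tolerability events mixed with scheduling and weight drift.

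**Working it through.** The plan gives no expected rate of delays or reductions, so there is no figure to reproduce. The check applies the SAP rules to dosing that complies with the protocol.

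**Inputs.** Delay limit 14 days and zero-tolerance reduction rule (SAP 7.2.3); ±2-day window (Schedules of Activities); recalculation required only beyond a 10% weight change, and rounding to two decimals (Protocol 5.4.1); dose levels (Protocol Table 2); 12-18 weeks on treatment (Protocol 3.1), which is about 6-9 two-week cycles.

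**1. Delay.** If the window runs from the previous dose, the longest compliant interval is 14 + 2 = 16 days. If it runs from a fixed calendar, a dose 2 days early followed by one 2 days late gives 14 + 4 = 18 days. Every compliant interval above 14 days is scored as a delay.

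If a share p of compliant intervals runs over 14 days, independently, a patient with k cycles has at least one false delay with probability 1 − (1 − p)^(k−1). The values of p are assumptions:

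| p | 6 cycles (5 intervals) | 9 cycles (8 intervals) |
|---|---|---|
| 5% | 1 − 0.95^5 = 23% | 1 − 0.95^8 = 34% |
| 10% | 1 − 0.90^5 = 41% | 1 − 0.90^8 = 57% |

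**2. Reduction.** With the mg dose unchanged after a weight gain g, derived mg/kg as a share of plan is 1/(1 + g).

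| Gain | Derived share of plan |
|---|---|
| 0.1% | 99.9% |
| 1% | 99.0% |
| 5% | 95.2% |
| 10% | 90.9% |

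Example: 3 mg/kg at 70 kg is 210 mg. At 76 kg (+8.6%, no mandatory recalculation), 210/76 = 2.76 mg/kg, scored as a 7.9% reduction.

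**3. Separation from real steps.** The largest false reduction is 1 − 1/1.10 = 9.1%. The smallest step down in Table 2 is from 10 mg/kg to the optional level of at most 6: (10 − 6)/10 = 40%. The others are 50% or more. A 90% cut-off therefore flags no compliant weight gain and misses no Table 2 step.

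**4. Rounding.** Section 5.4.1 says "the calculated dose will be rounded off to the second decimal point". At 0.01 mg/kg and 73.4 kg, 0.734 mg becomes 0.73 mg, and 0.73/73.4 = 0.00995 mg/kg. A zero-tolerance rule would flag this even with the weight used to prepare the dose.

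**5. Scope.** The delay rule applies to all parts. The weight rule applies to weight-based PF-04518600 with mg/kg prescribed and mg recorded. That is clearly Part A1. Part B1 is weight-based, but Section 5.4.3 describes adjustment at every cycle and does not repeat the discretion sentence. Parts A2 and B2 (Sections 5.4.2 and 5.4.4) and utomilumab are flat-dosed, so the weight problem cannot arise there.

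**The case against.** These are descriptive compliance tables. SAP 7.1 calls the summaries non-inferential, and delays and reductions are not listed among the endpoints. The reason table should place most scheduling and weight cases under Other, so the AE-attributed counts mostly survive. The by-cycle listing already shows cycle length and percentage of planned dose, from which a careful reader could separate false from real events. The CRF is not available to confirm how dose is recorded. If sites adjust for weight every cycle, as footnote 7 and the opening of 5.4.1 suggest, the weight-drift problem disappears. SAP Appendix 1 and Appendix 1.1 (derivations and visit windows) are marked TBD, so window handling is openly unfinished.

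Most of this stands and limits the consequence. It does not remove the point. Section 7.2.3 states definite rules, and the TBD appendices supply no tolerance to override them. The reason split does not correct the subject counts or the cycles before first event, and a compliant case with no recorded reason has no defined category.

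Three stronger readings are tempting:

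- **That the tables could mislead the MTD or RP2D choice.** No rule uses them. MTD rests on the DLT rate (Protocol 3.3 and 9.2.2), and Section 3.6 does not name them for the RP2D.
- **That Part B1 will show prohibited reductions.** Section 5.4.5.6.2 does say "Intrapatient dose reductions are not permitted during the combination therapy with PF-04518600 and utomilumab unless" the combination level is deemed above the MTD. Spurious cases would arise from weight drift only if B1 sites used the discretion that 5.4.1 gives for A1.
- **That nearly every patient will have a false delay.** Spreading intervals evenly over 12-16 days gives p = 2/5 and 1 − 0.6^5 = 92% over six cycles, but nothing in the documents supports an even spread.

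**Conclusion.** The point holds in limited form. In every part, a 15- or 16-day interval inside the window is scored as a cycle delay. In Part A1, and in B1 only if sites use the same discretion, a patient who gains up to 10% on an unchanged mg dose is scored as reduced, at 90.9-99.9% of plan for gains of 10% down to 0.1%. The harm is an inflated all-cause number (%) of subjects and distorted summaries of cycles before first delay or reduction. AE-attributed counts are largely protected; DLT, MTD and AE endpoints are unaffected.

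The size cannot be derived from the documents. The 23-41% for six cycles assumes that 5-10% of intervals run 15-16 days, independently. The weight half also depends on how many sites leave the dose unchanged and how weights move. Real events are still captured; the fault is that compliant dosing is counted with them.

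**What to change.** Amend SAP 7.2.3 before database lock.

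- **Dose reduction:** count one only when derived mg/kg is below 90% of the planned dose, or when a dose-level reduction is recorded. Do not rely on a zero-tolerance comparison, even with the preparation weight, because rounding can still trip it at 0.01 mg/kg.
- **Cycle delay:** count one only when Day 1 falls beyond the protocol's 2-day window, and state the anchor: more than 16 days if the window runs from the previous dose, or more than 2 days after the scheduled date if it is calendar-anchored. Still count any delay recorded with an AE reason, so that short toxicity delays are kept.
- **Protocol text:** footnote 7 of the schedules and the opening of 5.4.1, which describe weight adjustment at every cycle, must be reconciled with the site-discretion sentence in 5.4.1.

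The cost is two revised SAP definitions, a small programming change and the protocol clarification. The main downside is that 1-2 day delays without an AE reason would appear only in the by-cycle listing. A shortfall of up to 10% from another cause, with no recorded step, would likewise appear only as percentage of planned dose.
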